10.4 End-of-Study Definition

A clinical trial is considered completed when participants are no longer being examined or the last participant's last study visit has occurred.

Subjects will be followed through 30 days post index procedure. At study completion, an End of Study form will be completed. The end of study is defined as completion of the last visit or a reason for the last study visit not having been completed has been determined by the investigator or designee. If the last follow up visit was not completed, the investigator will note the reason on the study completion form (e.g. subject withdrawn by investigator, subject withdrew consent, lost to follow-up, AE, death, etc.)

11 Study Methods

11.1 Data Collection

The data collection schedule is shown in Table 10-1.1.

Table 10-1.1: Data Collection Schedule

Procedure/Assessment	Screening	Baseline	Study Procedure	30 Days (± 5 days) Follow Up
Informed consent process, including informed consent signature date	X			
Demographics, Medical History		X		
Procedure			X	
Device Deficiency Assessment			X	X
Adverse Event Assessment			X	X
End of Study			X	X

X=required

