7.1. Primary effectiveness endpoints

Initial Cohort

Ability to complete the indication for the use of endoscopic clipping

Continued Enrollment Cohort

Clinical success defined as, where applicable,

- Absence of delayed bleeding
- Sustained closure of the targeted leasion (up to 30 days after the endoscopic clipping procedure)

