7.2. Primary Safety endpoint

Rate of serious adverse events (SAEs) related to the MANTISTM clip or the endoscopic study portion of the procedure.

NOTE: If providing hemostasis to an active bleeding in Group A requires possible additional hemostasis after the index study procedure for management of bleeding SAEs within 7 days of the index study procedure, then such bleeding SAEs are not counted for the Primary Safety Endpoint.

Additional endpoints:

- Technical success at placement defined as ability to deploy the endoscopic clips in satisfactory position.
- Ability to anchor device, mobilize the tissue, and approximate defect edges for a secured closure.
- Post procedural bleeding, defined as a severe bleeding event that required hospitalization, a blood transfusion (>5 units), or another invasive intervention (angiographic or surgical) within 30 days after completion of the study clip placement procedure.

- For active bleeding hemostasis cases only
 - o Rate of patients requiring additional modalities of hemostasis.
 - Report of hemostasis of active bleeding 7 days after the index study procedure, and/or with additional clipping procedures to provide hemostasis of continued or recurrent bleeding within 7 days of the index study procedure

8. Study Design

Prospective, multi-center, multi-national, open label, consecutive enrollment. The population will be split up into 5 groups, namely:

- Group A: Hemostasis
- Group B: Closure
- Group C: Anchoring
- Group D: Endoscopic Marking
- Group E: Other

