8.1 Scale and Duration

Scope of the series:

- Initial Cohort:
 - o Up to 50 cases
- Continued Enrollment Cohort:
 - o Up to 240 cases not including Initial Cohort
- Up to 15 sites

The study duration for each subject is expected to be approximately 1 month. Enrollment is expected to be completed in approximately 18 months per cohort.

Study visits:

- Screening/Enrollment and Baseline: Informed consent process, including informed consent signature date
- Procedure
- 30-day follow-up Telephone Interview

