11.6 Study Procedure

During the index procedure, the endoscopist or designated member of study staff will record: Clip information, and any activities completed or attempted during the procedure, regardless of original intent. Any ensuing adverse or device events will be recorded and reported.

11.7 30 Day (± 5 days) Telephone Interview Assessments

All enrolled subjects will be evaluated via telephone to screen for any post-procedure adverse events, and to evaluate the resolution of any previously noted adverse events or sequelae, as applicable.

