12.1 Endpoints

12.1.1 Primary Endpoints

12.1.1.1 Primary Effectiveness Endpoint:

Initial Cohort

Ability to complete the indication for the use of endoscopic clipping

Continued Enrollment Cohort

Clinical success defined as, where applicable,

- Absence of delayed bleeding
- Sustained closure of the targeted leasion

up to 30 days after the endoscopic clipping procedure

12.1.1.2 Primary Safety Endpoint:

Rate of serious adverse events (SAEs) related to the MANTISTM clip or the endoscopic study portion of the procedure.

NOTE: If providing hemostasis to an active bleeding in Group A requires possible additional hemostasis after the index study procedure for management of bleeding SAEs within 7 days

of the index study procedure, then such bleeding SAEs are not counted for the Primary Safety Endpoint.

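### The primary effectiveness endpoint needs 30 days of observation, but the only follow-up call may be made, and the subject's study closed, from day 25, and the SAP has no rule for the shorter follow-up

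*Protocol*

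**What the plan says.** **Endpoint.** Protocol Section 12.1.1.1 defines clinical success in the continued enrollment cohort as absence of delayed bleeding and sustained closure, where applicable, "up to 30 days after the endoscopic clipping procedure". Section 7.1 attaches the limit to the closure item: "Sustained closure of the targeted leasion (up to 30 days after the endoscopic clipping procedure". SAP Section 3.1.1 does the same. The additional endpoint of post-procedural bleeding, listed in Protocol Section 7.2, is counted "within 30 days after completion of the study clip placement procedure".

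**Length of follow-up.** Protocol Section 10.4: "Subjects will be followed through 30 days post index procedure". The same section places the end of study at completion of the last visit.

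**Schedule.** Section 8.1 lists one contact after the procedure, the "30-day follow-up Telephone Interview". Table 10-1.1 in Section 11.1 gives its timing as "30 Days (± 5 days) Follow Up", and Sections 11.7 and 11.8 repeat the tolerance. On the content of the call, Section 11.7 says: "All enrolled subjects will be evaluated via telephone to screen for any post-procedure adverse events".

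**Analysis.** SAP Section 7.3 reports binary rates per patient, defines a last follow-up date and gives imputation rules for adverse event onset dates. It does not connect the last follow-up date to the classification of either primary endpoint.

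**Safety.** The primary safety endpoint is the "Rate of serious adverse events (SAEs) related to the MANTISTM clip or the endoscopic study portion of the procedure". It has no stated time limit. Its only time element is the 7-day exclusion of certain bleeding events.

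**The concern.** A tolerance of 5 days either side of day 30 is harmless for a measurement taken at a visit. Here the call is instead the last scheduled look at an interval that closes on day 30. The late half of the tolerance (days 30 to 35) covers the whole interval. The early half (days 25 to 29) does not, and no later contact is planned. For a subject called early, the Section 10.4 statement and the Table 10-1.1 window cannot both hold.

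The stake is the test of clinical success against the fixed 89% goal. If a subject with no reported event at an early call is scored a success, any failure between the call and day 30 is lost, and the loss can only raise the observed success rate. The study has one arm, so there is no control group in which the same loss could cancel.

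**Working it through.** **1. Size of the gap.** Earliest call: 30 − 5 = day 25. Days 26 to 30 are then unobserved: 5 of 30 days, or 16.7% of the interval. A call on day 29 leaves one day unobserved. A call on day 30 or later leaves none.

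**2. The plan's own figure.** Inputs from SAP Section 3.1.3: goal 89%, expected rate 94%, exact test, alpha 0.05 (taken one-sided, as the hypotheses are), 217 evaluable subjects, power at least 80%. The smallest passing count is 201 successes:

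- P(Bin(217, 0.89) ≥ 201) = 0.0492. At 200 it would be 0.0788, above 0.05.
- P(Bin(217, 0.94) ≥ 201) = 0.841.

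The stated power holds. The window does not alter the sample size.

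**3. Effect of unseen failures, if they are scored as success.** The documents give neither the timing of failures nor the call dates, so two quantities are assumed:

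- f, the share of 30-day failures that fall on days 26 to 30;
- u, the average share of those late failures that falls after the subject's call.

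At a true success rate of 89% the observed rate is 1 − 0.11 × (1 − f × u), and the chance of passing is P(Bin(217, that rate) ≥ 201).

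Three patterns of call dates:

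- **Calls spread evenly over the 11 days 25 to 35, late failures spread evenly over days 26 to 30.** Calls on days 25, 26, 27, 28 and 29 miss 5, 4, 3, 2 and 1 of the five days. So u = (5 + 4 + 3 + 2 + 1) / (5 × 11) = 15/55 = 0.273.
- **Half the calls on day 25, the rest on day 30 or later:** u = 0.5.
- **All calls on day 25 (worst case):** u = 1.

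For f, 16.7% is a constant hazard over 30 days; 5% and 10% represent failures that come mostly earlier.

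Example, even spread and f = 10%: observed rate = 1 − 0.11 × (1 − 0.0273) = 0.8930, and the chance of passing is 0.0647.

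| Chance of passing at true 89% (nominal 4.9%) | f = 5% | f = 10% | f = 16.7% |
|---|---|---|---|
| Calls even over days 25 to 35 | 5.7% | 6.5% | 7.7% |
| Half of calls on day 25 | 6.3% | 8.0% | 10.9% |
| All calls on day 25 | 8.0% | 12.6% | 21.6% |

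**4. In subjects.** Expected missed failures are 217 × 0.11 × f × u. With calls spread evenly this is 0.3 (f = 5%), 0.7 (f = 10%) or 1.1 (f = 16.7%). In the worst cell it is 217 × 0.11 × 0.167 × 1 = 4.0.

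**The case against.** **Day 30 can be read as a nominal visit.** Section 11.8 itself states follow-up as 30 days with the 5-day tolerance, and a symmetric window is ordinary practice. That explains the window, but it does not reconcile it with an endpoint and a Section 10.4 statement that both run to day 30.

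**The call is not the only way events are found.** Sites must report serious adverse events as they learn of them (Protocol Sections 19.1 and 19.4), and onset dates are already recorded. This narrows the gap but does not close it: reporting runs to the end of the study, which for a subject can be read as the call itself.

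**The large figures need unlikely call dates.** This stands. Nothing suggests that half or all of the calls would fall on day 25. The even spread is the more reasonable central case, and its effect is small.

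**Stronger readings that the documents do not support:**

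- *Both primary endpoints are cut short of day 30.* Only effectiveness carries a 30-day limit. The 30-day wording in Section 7.2 belongs to the additional post-procedural bleeding endpoint. Primary safety has no stated window, and a call on days 31 to 35 could add related events, so no net direction of bias can be claimed for it.
- *The plan counts unseen events as success.* No text says so. The plan is silent: it does not classify such a subject as a success, a failure or missing.

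**Conclusion.** The point holds for the primary effectiveness endpoint, and the additional post-procedural bleeding endpoint has the same gap. The visit window allows a subject's observation to end up to 5 days before the endpoint does, and the SAP does not say what then happens.

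The upward bias in the success rate depends on reading no reported event as success. Its size depends on call dates and failure timing, neither of which the documents give. Under evenly spread calls the chance of passing at a true 89% is 5.7% to 7.7% against a nominal 4.9%, or about 0.3 to 1.1 missed failures in 217. The 21.6% figure is a bound that needs every call on day 25 and a constant hazard; it is not an expectation. Severity: minor, and worth correcting because the correction is cheap.

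**What to change.** 1. **Protocol Table 10-1.1 and Sections 11.7 and 11.8:** change the data-collection window for the call from 30 ± 5 days to day 30 to day 35, or to day 40 to keep the present width.
2. **SAP Section 3.1.1:** state that effectiveness events count only if their onset is on or before day 30, using the onset dates already collected. This stops a later call from lengthening the endpoint.
3. **SAP, for subjects already contacted before day 30:** add a sensitivity analysis that treats them as followed only to the day of contact.

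The cost is a short amendment, a changed window setting in the electronic data capture system and one extra analysis. The sample size is unaffected. The downside is slightly later calls and, with the narrower window, possibly a few more contacts out of window. If enrollment is too far advanced to change the window, item 3 can be done alone.

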11.2 Study Candidate Screening

No study-specific data will be collected until after the subject has signed an Informed Consent Form (ICF). A Screen Failure/Enrollment Log will be maintained in the EDC system by the center to document select information about candidates who signed consent.

11.3 Strategies for Recruitment and Retention

All patients under the care of a study investigator during the enrollment period of a site will be considered for recruitment.

11.4 Informed Consent

Data collection will not occur prior to the subject signing the ICF. Patients will be considered enrolled in the study once they sign the ICF. Once a subject is considered enrolled in the study, baseline information may be obtained.

11.5 Baseline

Baseline information will include the following data points: age at time of consent, gender, and relevant medical history.

11.6 Study Procedure

During the index procedure, the endoscopist or designated member of study staff will record: Clip information, and any activities completed or attempted during the procedure, regardless of original intent. Any ensuing adverse or device events will be recorded and reported.

11.7 30 Day (± 5 days) Telephone Interview Assessments

All enrolled subjects will be evaluated via telephone to screen for any post-procedure adverse events, and to evaluate the resolution of any previously noted adverse events or sequelae, as applicable.

11.8 Study Completion

Subjects will be followed for 30 days (\pm 5 days) post index procedure. Subjects will continue to receive care from their doctor as they normally would. At study completion, an End of Study form will be completed, indicating whether the subject completed the study. If the last follow-up visit was not completed, the reason will be noted on the study completion form (e.g. subject withdrawn by investigator, subject withdrew consent, lost to follow-up, AE, death, etc.) and a Protocol Deviation form will be completed.

11.9 Source Documents

It is preferable that original source documents are maintained, when available. In lieu of original source documents, certified copies are required to be maintained. A certified copy is a copy (irrespective of the type of media used) of the original record that has been verified (i.e., by a dated signature or by generation through a validated process) to have the same information, including data that describe the context, content, and structure, as the original.

12 Statistical Considerations

12.1 Endpoints

12.1.1 Primary Endpoints

12.1.1.1 Primary Effectiveness Endpoint:

Initial Cohort

Ability to complete the indication for the use of endoscopic clipping

Continued Enrollment Cohort

Clinical success defined as, where applicable,

- Absence of delayed bleeding
- Sustained closure of the targeted leasion

up to 30 days after the endoscopic clipping procedure

12.1.1.2 Primary Safety Endpoint:

Rate of serious adverse events (SAEs) related to the MANTISTM clip or the endoscopic study portion of the procedure.

NOTE: If providing hemostasis to an active bleeding in Group A requires possible additional hemostasis after the index study procedure for management of bleeding SAEs within 7 days

of the index study procedure, then such bleeding SAEs are not counted for the Primary Safety Endpoint.

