12.1.1.3 Hypotheses and Sample Size Justification

Initial cohort:

No hypotheses will be tested, only observational, summary statistics will be performed.

Continued enrollment cohort:

A systematic literature search was conducted on PubMed and Embase from January 1, 2016 to September 2022 to identify studies that evaluated the safety and effectiveness of an endoscopic clip device for closing various types of incisions, lesions, or defects in the gastrointestinal tract resulting from endoscopic mucosal resection (EMR), endoscopic submucosal dissection (ESD), polypectomy of polyps or adenomas, perforations, and fistulas. The primary objective of the search strategy was to identify studies that examined the closure of large mucosal defects by endoscopic clipping. Twenty studies were identified through a post-market literature review activity were included to the analysis with a total of 2257 patients.

We hypothesize that the **clinical success rate** of MANTISTM clip will be greater than the performance goal of **89%** with expected clinical success rate of **94%**. These assumptions are based in the following meta-analyses of clinical success for closure of a defect:

• 20 publications representing 2257 patients: 93.9% (95% CI 88.6%-97.6%)

We hypothesize that the **serious adverse event (SAE) rate** related to MANTISTM clip or the endoscopic clipping portion of the procedure will be lower than the performance goal of **19%** with expected related SAE rate of **10%**. These assumptions are based in the following meta-analyses of clinical success for closure of a defect:

- 9 publications representing 1019 patients: 9.8% (95% CI 3.7%-18.5%)
 - 12.2 Using an exact test with an alpha level of 0.05, 217 subjects enrolled will provide at least 80% power for the performance and safety metrics. An additional 10% will be added for attrition, so total enrollment will be 240 subjects. These tests will only be performed for cases in the continued enrollment cohort General Statistical Methods

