	NOTE: If providing hemostasis to an active bleed requires possible additional hemostasis after the index study procedure for management of bleeding SAEs within 7 days ³⁶ of the index study procedure, then such bleeding SAEs are not counted for the Primary Safety Endpoint.	
Additional Endpoints	Technical success at placement defined as ability to deploy the endoscopic clips in satisfactory position.	
	2. Ability to anchor device, mobilize the tissue, and approximate defect edges for secured closure. (Group B only).	

MANTIS Clip Study		
	3. Post procedural bleeding, defined as a severe bleeding event that required hospitalization, a blood transfusion (>5 units), or another invasive intervention (angiographic or surgery) within 30 days after the study clip placement.	
	4. For active bleeding hemostasis cases only	
	a. Rate of patients requiring additional modalities of hemostasis.	
	b. Report of hemostasis of active bleeding 7 days after the index study procedure, defined as ability to stop the active bleed at the time of the study procedure and/or with additional clipping procedures to provide hemostasis of continued or recurrent bleeding within 7 days of the index study procedure	
Follow-up Schedule	Baseline	
	Procedure	
	30 day follow up (both Initial and Continued Enrollment Cohort)	
Study Duration	Enrollment is expected to be completed in approximately 18 months; therefore the total study duration is estimated to be approximately 19 months as Subjects will be on the study for up to 30 days.	
Key Inclusion Criteria	Subject indicated for endoscopic clipping per local standard of practice.	
	2. Willing and able to comply with the study procedures and provide written informed consent to participate in the study.	
	NOTE: Hemostasis and closure can be needed in the setting of complications such as perforations or acute bleeding that are typically rare and sometimes emergent. In such circumstances consenting the patient before the procedure is not feasible and consent shall be obtained from the patient after the procedure but before any study data is collected.	
Key Exclusion Criteria	1. Subjects who are currently enrolled in another investigational study that would directly interfere with the current study, without prior written approval from the sponsor.	

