3.1.3 Hypotheses and Sample Size

Initial cohort:

No hypotheses will be tested, only observational, summary statistics will be performed.

Continued enrollment cohort:

A systematic literature search was conducted on PubMed and Embase from January 1, 2016 to September 2022 to identify studies that evaluated the safety and effectiveness of an endoscopic clip device for closing various types of incisions, lesions, or defects in the gastrointestinal tract resulting from endoscopic mucosal resection (EMR), endoscopic submucosal dissection (ESD), polypectomy of polyps or adenomas, perforations, and fistulas. The primary objective of the search strategy was to identify studies that examined the closure of large mucosal defects by endoscopic clipping. Twenty studies

were identified through a post-market literature review activity were included to the analysis with a total of 2257 patients.

We hypothesize that the **clinical success rate** of MANTISTM clip will be greater than the performance goal of **89%** with expected clinical success rate of **94%**. These assumptions are based in the following meta-analyses of clinical success for closure of a defect:

• 20 publications representing 2257 patients: 93.9% (95% CI 88.6%-97.6%)

The null and alternative hypotheses for the primary effectiveness endpoint are as follows:

Ho: $\pi_1 \le 89\%$ *Ha*: $\pi_1 > 89\%$

where π_1 is the probability of clinical success.

We hypothesize that the **serious adverse event (SAE) rate** related to MANTISTM clip or the endoscopic clipping portion of the procedure will be lower than the performance goal of **19%** with expected related SAE rate of **10%**. These assumptions are based in the following meta-analyses of clinical success for closure of a defect:

• 9 publications representing 1019 patients: 9.8% (95% CI 3.7%-18.5%)

The null and alternative hypotheses for the primary endpoint are as follows:

Ho: $\pi_1 \ge 19\%$ *Ha*: $\pi_1 < 19\%$

where π_1 is the probability of an related SAE.

Using an exact test with an alpha level of 0.05, 217 subjects enrolled will provide at least 80% power for the performance and safety metrics. An additional 10% will be added for attrition, so total enrollment will be 240 subjects. These tests will only be performed for cases in the continued enrollment cohort

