5.6 Subgroup Analyses

Stratified analyses will include tabulating the primary and select secondary endpoints by gender, polyp location, polyp size, or use of periprocedural antithrombotic medications.

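### The effectiveness test pools Groups A–E against a defect-closure goal, with no rule for cases that have nothing to close and no bleeding or resection site

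*Protocol*

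**What the plan says.** Protocol 12.1.1.1 and SAP 3.1.1 give the continued-cohort endpoint in the same terms: "Clinical success defined as, where applicable", then two components, absence of delayed bleeding and sustained closure of the target up to 30 days. The protocol synopsis, Protocol 7.1 and the SAP summary repeat it. None says which component applies to which kind of case.

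The cohort is broad. Under Protocol 8, "The population will be split up into 5 groups, namely" hemostasis, closure, anchoring, endoscopic marking and other. Inclusion criterion 1 admits any subject with an indication for clipping, and Protocol 6 describes consecutive cases in which at least one study clip is selected.

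The goal is narrow. Of the 89% goal and the 94% expected rate, Protocol 12.1.1.3 says: "These assumptions are based in the following meta-analyses of clinical success for closure of a defect".

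On who is tested, SAP 3.1.3 says only: "These tests will only be performed for cases in the continued enrollment cohort". The analysis sets (Enrolled, ITT, Treated) are not endpoint-specific, and none is assigned to the primary test. SAP 7.3 adds only that proportions are per patient.

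On breakdowns, SAP 5.6 states: "Stratified analyses will include tabulating the primary and select secondary endpoints by gender, polyp location, polyp size, or use of periprocedural antithrombotic medications". Group A–E is not among these strata. Some additional endpoints are restricted by use. The SAP summary limits one to cases where the task is to "approximate defect edges for secured closure. (Group B only"), and others apply to active bleeding only.

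**The concern.** A marking or anchoring case may have nothing to close and no site expected to bleed. For such a case the definition can be read in three ways:

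- **(a)** No component fails, so the case is a success.
- **(b)** It is scored on delayed bleeding alone. This is feasible because, under Protocol 11.7, "All enrolled subjects will be evaluated via telephone to screen for any post-procedure adverse events". The result is a near-automatic success.
- **(c)** No component applies, so the case leaves the denominator.

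Under (a) or (b) these cases raise the pooled rate, and the test can pass while the cases with something to close or bleed only equal the goal. Under (c) the tested number falls below the 217 used for the power statement. The study is open label, so an unstated rule could be settled after outcomes are known. With no tabulation by group, a reader could not see how the primary result differs between closure cases and the rest.

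**Working it through.** **Inputs.** Goal 0.89, expected rate 0.94, exact test, alpha 0.05, 217 subjects (Protocol 12.1.1.3, SAP 3.1.3). The hypotheses are directional, so the test is taken as one-sided at 0.05. The share of no-component cases is not documented. I assume 5% and 10% of 217, with 2% and 20% as an outer range. This gives k = 4, 11, 22 or 43 such cases and m = 217 − k = 213, 206, 195 or 174 applicable cases.

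**The plan's own figure.** The smallest r with P(Bin(217, 0.89) ≥ r) ≤ 0.05 is r = 201, with attained size 4.9%. Power is P(Bin(217, 0.94) ≥ 201) = 84.1%. The plan's claim of at least 80% is reproduced.

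**Reading (a), automatic success.** The chance of passing when applicable cases succeed at exactly 89% is P(Bin(m, 0.89) ≥ 201 − k).

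**Reading (b), bleeding only.** Successes are the sum of Bin(k, 1 − b) and Bin(m, 0.89). I take P(sum ≥ 201), with b the assumed delayed-bleeding rate in the no-component cases.

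**Reading (c), excluded.** The exact critical value is recomputed at m, and power is taken at 0.94.

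| Assumed share | m | (a) pass at 89% | (b) b = 2% | (b) b = 5% | (c) power at 94% |
|---|---|---|---|---|---|
| 0% | 217 | 4.9% | – | – | 84.1% |
| 2% | 213 | 5.9% | 5.7% | 5.4% | 78.9% |
| 5% | 206 | 8.0% | 7.4% | 6.5% | 82.4% |
| 10% | 195 | 12.6% | 10.8% | 8.4% | 80.5% |
| 20% | 174 | 26.7% | 20.7% | 13.5% | 75.3% |

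The 78.9% at 213 is saw-tooth in the exact test: power is already 77.3% at 216. Only the 20% row shows a real loss.

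**Where the verdict depends on the rule, (a) against (c).**

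- 5% share: (a) needs 201 − 11 = 190 of 206, and (c) needs 191. A result of exactly 190 gets opposite verdicts. Its probability is about 3%, 10% or 6% at a true applicable rate of 89%, 92% or 94%.
- 10% share: (a) needs 201 − 22 = 179 of 195, and (c) needs 181. Results of 179 or 180 get opposite verdicts, with probability about 8%, 21% or 12% at the same rates.

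Scoring no-component cases as failures is not a workable reading. At a 10% share only 195 successes would be possible and 201 are needed.

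**The case against.** The best defence is that the definition already implies (c): a case is judged on the components that apply, so a case with none is not evaluable. On that reading the plan loses little, since power is 82.4% or 80.5% at 5% or 10% shares. Those figures also assume that the whole attrition allowance from 240 to 217 is used, although follow-up is a single telephone call. The listed continued-cohort objectives are all prophylaxis or closure, and the SAP summary words them as specific aims, which points to a low share. The larger pass probabilities need both automatic success and a sizeable share.

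Most of this stands as a limit on size. It does not remove the gap. Exclusion is implied at most: no evaluable set exists, the protocol leaves its list of objectives open-ended, and the allowance above 217 is for attrition only.

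Group counts could be reported from procedure data, because Protocol 11.6 records "any activities completed or attempted during the procedure, regardless of original intent". The polyp strata show part of the resection subset. What is not planned is the primary result by group.

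A reader might infer that every anchoring and marking case is certain to be in the denominator. The text does not say so: restricting the tests to the continued cohort rules out the Initial Cohort and settles nothing more. A reader might also call the 8.0% or 12.6% an inflated type I error. It is not one for the stated cohort-wide hypothesis, because the pooled rate would then truly exceed 89%.

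**Conclusion.** The concern holds in a limited form. The rule for no-component cases is missing from the primary endpoint. It changes the denominator, and it changes what a pass says about a closure-derived goal.

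The size depends on an undocumented case mix. As upper bounds under automatic success, the chance of passing with applicable cases at exactly 89% is 5.9%, 8.0% or 12.6% at shares of 2%, 5% or 10%, against 4.9%. Under exclusion the power loss is minor unless the share is large. The verdict depends on the rule in roughly 3–10% of trials at a 5% share and 8–21% at a 10% share, for true applicable rates of 89–94%.

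The documents do not support calling the study underpowered on this account, nor do they make all-comer enrolment a flaw; it is deliberate. This should be fixed before data review. Confidence is medium because the shares are assumed.

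**What to change.** 1. In Protocol 12.1.1.1 and SAP 3.1.1, state which component applies to each of Groups A–E, including which Group E cases have one. Set the effectiveness denominator as continued-cohort subjects whose planned indication has at least one applicable component. Planned indication is preferable to actual clip use, because subjects planned for a clip but not given one then stay in. List the no-component cases by group and never count them as successes. Restate exact power for the number expected in this set.
2. In Protocol 12.3.6 and SAP 5.6, add Group A–E to the strata for both primary endpoints, with exact confidence intervals. Closure and prophylaxis results can then be seen descriptively beside the closure-derived goals. This matters even after step 1, because active-bleeding cases stay in a test whose goal comes from closure. Prophylaxis is listed under hemostasis in the indications, so separating it within Group A depends on the recorded procedure activities.

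Formal comparison of subsets with 89% or 19%, and a rule on how an all-comer pass is described, are optional. The safety test may stay on all treated continued-cohort subjects.

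The cost is wording in both documents, a slightly smaller tested set and possibly a lower stated power. The groups are already defined, and no added enrolment is needed for the wording change.
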